We will conduct a cross-sectional online survey with a nationally representative probability-based sample of adults (ages 18-65) recruited from the AmeriSpeak panel, funded and operated by NORC at the University of Chicago. All panel members aged 18-65 will be invited to be screened, and those who have used CBD in the past 30 days (current users), those who have ever used CBD (ever), and those who have never used CBD (non-users) will be invited to participate. We will assess consumer perceptions of documented health claims made inside CBD retailers. Given NORC's estimated response rate of 34% and prevalence estimates for CBD use between 14-25%, we estimate a random sample of 22,000 adults will be screened to achieve our goal of 3,000 completed surveys consisting or 1,000 current CBD users, 1,000 ever CBD users, and 1,000 non-users. AmeriSpeak participants will receive points, worth approximately \$5, for completing the survey. No incentive will be provided for completing the screener. Although our goal is to have 3000 completed surveys, we anticipate having up to 600 additional completed surveys since this is an online survey and we will allow anyone who is taking the survey to complete it and receive the incentive. We will monitor the number of completed surveys by user status on a daily basis to achieve the targeted goal of 3000 completes and minimize additional surveys over the targeted goal. Thus, our sample size is n=3525. We will assess data quality by ensuring participants meet sufficient completion criteria. Participants must have met both of the following criteria to be included in the study: 1) at least 75% of the outcome variables answered (not skipped) and 2) survey completion time of > 5min. All completed surveys will be used in data analysis.

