To assess eligibility, participants will be asked their age and several questions about CBD use. If eligible, participants will be invited to complete the full survey. For the survey, participants will be randomly assigned to a panel consisting of up to 10 CBD advertisements that include FDA prohibited or potentially-prohibited claims. Participants will complete questions while the stimuli are shown on the survey webpage. After the interview, participants will receive a link to electronic resources with up-to-date CBD information based on the literature, guidance documents from the Food and Drug Administration (FDA), and organizations including the Center for Disease Control (CDC) and Substance Abuse and Mental Health Services Administration (SAMHSA).

Setting

Survey participants will complete the online survey in a location of their choosing.

Subjects Selection Criteria

AmeriSpeak is an active panel, funded and operated by NORC at the University of Chicago that is designed to be representative of the U.S. household population. U.S. households are randomly selected within NORC's National Sample Frame and supplemented by address-based sample frames. This is conducted through a two-stage sampling process. The first stage is the primary sampling unit, which is a National Frame Area of an entire metropolitan area or county. The second stage occurs within this sampling unit. Secondary sampling

units are segments defined from Census tracts or block groups. Within these segments, all housing units are listed using the U.S. Postal Service Delivery Sequence File. The final National Frame contains approximately 3 million households. Selected households are invited to join AmeriSpeak™ by telephone or by web, and participate in research studies 2-3 times a month. For this study, all 18-65 year old panel members will be screened by AmeriSpeak™. Individuals who are a current CBD user within the past 30 days will be invited to participate in the study. We will also include a sample of ever-CBD and non-CBD users to understand consumer perceptions from those who do not currently use, as well. We will oversample CBD users so the final respondent sample is comprised of 1/3 current CBD users, 1/3 ever CBD users, and 1/3 never-users. It is expected that AmeriSpeak™ will screen 22,000 adults to obtain the sample size.

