To assess drug effect claims, all participants will be asked "How much does this ad suggest that CBD can cure, prevent, or treat a health condition?"

To assess FDA endorsement claims, participants will be asked "How much does this ad suggest that the advertised CBD is approved or endorsed by the US Food and Drug administration (FDA)?"

To assess dietary supplement or vitamin claims, participants will be asked "How much does this ad suggest that CBD is a dietary supplement or vitamin?"

To assess food additive claims, participants will be asked "How much does this ad suggest CBD is a main ingredient in a food or beverage?

To assess if a claim is false and misleading participants will be asked "How much does this ad suggest the information shown is based on scientific evidence?" and "How much would this ad appeal to youth under the age of 18?"

We will also assess perceived product safety, appealand perceived benefits, outcome expectancies, and willingness to try CBD (non-CBD users only). For CBD users, we will ask additional questions about their use of CBD (i.e. frequency, product type, reasons for use, and use with other cannabinoids). All participants will be asked about their demographic and health status.

Analytic Plan

The goals of the analysis are to 1) determine if CBD use status is associated with interpreting our main outcome and secondary outcomes (main = claim perception as one of the prohibited claim types, secondary = appeal of advertisements and perceived product safety); 2) identify which claims are interpreted by consumers in ways that the FDA has determined are prohibited; and 3) explore participant characteristics (beyond use status) that are associated with interpreting a claim as one of the prohibited claim types.

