First, analyzing all claims together, we will assess the mean score for each claim type (i.e. drug effect; FDA approved/endorsed; dietary supplement; food additive; false/misleading-youth; false/misleading-science) to determine if CBD use status is associated with interpreting ads as containing one of the prohibited claim types. We will also assess the mean for perceived product safety and appeal by use status. For each of the advertisements, we will then estimate the proportion of participants that interpret the claim as one or more of the prohibited claim types (i.e. drug effect, FDA approved/endorsed; dietary supplement; food additive; false and misleading). Chi-squared tests will compare proportions between CBD users and non-users. Next, analyzing all claims together, we will model the likelihood of interpreting a claim as a prohibited claim type as a function of CBD use status, sex, race/ethnicity, claim meaning score, and chronic health conditions using random-effects logistic regression modeling to account for the repeated measures within an individual. Odds ratios from the models will be used to identify differences between groups in their perceptions of claims. All statistical tests will be two-sided with a 0.05 significance level and all analyses will be performed using SAS V9.4.

Human Subjects Protection

Subject Recruitment Methods

Participants will be recruited and screened by AmeriSpeak™ according to age (18-65) and CBD use status (current CBD (users within the last 30 days), ever CBD users, and non-users). All panel members who are 18-65 years old will be screened for the survey, and those who are classified as a CBD user, ever user, or non-user will be invited to participate in the study. Eligible participants will continue to review the informed consent and complete the full survey.

Informed Consent

A waiver of signed consent/assent s requested. This is an online survey and individual participation involves providing voluntary responses to survey questionnaires. The research presents no more than minimal risk of harm to subjects. Consent language will be included in the survey and participants will be asked to check a box to indicate that they agree to participate.

Confidentiality and Privacy

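### Neither pooled analysis by CBD use status has an advertisement term, although participants are randomised to panels of advertisements; adding one is a small, free improvement and settles which odds ratio is estimated

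*Combined protocol and SAP*

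**What the plan says.** In the combined protocol and SAP, the Design section states that "participants will be randomly assigned to a panel consisting of up to 10 CBD advertisements". It gives neither the number of panels nor the number of advertisements. That panels differ in content is an inference from random assignment to a panel.

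The Analytic Plan has three steps:

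- **Pooled mean scores by use status.** "First, analyzing all claims together, we will assess the mean score for each claim type". No model, covariates or unit of analysis are named.
- **Per-advertisement proportions.** "For each of the advertisements, we will then estimate the proportion of participants" reading it as a prohibited claim type, with chi-squared tests.
- **Pooled logistic model.** The likelihood of a prohibited reading is modelled "as a function of CBD use status, sex, race/ethnicity, claim meaning score, and chronic health conditions". The only random effect named is for the participant, to allow for several ratings by one person. Its odds ratios are to be used to identify differences between groups.

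The advertisement therefore enters only the second step. Yet the second stated goal of the analysis is to "identify which claims are interpreted by consumers in ways that the FDA has determined are prohibited", so the plan itself looks for differences between advertisements.

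**The concern.** If advertisements differ in how they are read, a participant's average rating depends partly on the panel drawn. Leaving the advertisement out of the pooled analyses puts that variation into the error.

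Two things follow. The mean-score comparison loses some precision that the design would give back at no cost. The logistic model, which has a participant effect but no advertisement effect, estimates an odds ratio averaged over advertisements. Because odds ratios are not collapsible, this lies closer to 1 than the odds ratio for a given advertisement. The plan does not say which of the two is meant, and both bear on its main question, claim perception by use status. The per-advertisement step is not affected.

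**Working it through.** **Inputs.** From the documents: random assignment to panels of up to 10 advertisements, 3,525 surveys, and use-status groups of one third each. The documents give no SD, intraclass correlation, effect size or power, so there is no figure of the plan's own to reproduce on this point. All variance shares, panel counts and logit SDs below are assumptions.

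**1. Mean scores.** Let p, a and e be the person, advertisement and residual shares of rating variance (p + a + e = 1), m the advertisements per panel and K the number of panels, with advertisements allocated to panels at random. The variance of a participant's mean is

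- with the term: p + e/m
- without it: p + e/m + ((K−1)/K) × a/m

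The factor (K−1)/K is there because participants share K fixed panels and do not each draw fresh advertisements. Group size cancels in the ratio. The survey equivalent is 3,525 × (1 − 1/ratio).

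| K | p | a | with term | added | increase | surveys |
|---|---|---|---|---|---|---|
| 8 | 0.30 | 0.10 | 0.30 + 0.060 = 0.360 | 0.00875 | 2.4% | 84 |
| 8 | 0.30 | 0.20 | 0.30 + 0.050 = 0.350 | 0.01750 | 5.0% | 168 |
| 2 | 0.30 | 0.10 | 0.360 | 0.00500 | 1.4% | 48 |
| 2 | 0.30 | 0.20 | 0.350 | 0.01000 | 2.9% | 98 |

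(m = 10 throughout.) With K = 8 and p from 0.15 to 0.45, the increase runs from 0.00875/0.225 = 3.9% down to 0.00875/0.495 = 1.8% for a = 0.10. For a = 0.20 it runs from 0.0175/0.215 = 8.1% down to 0.0175/0.485 = 3.6%. Panels balanced by claim type would give less. If all panels were identical, there would be no gain with complete ratings.

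In power terms, a comparison with 80% power without the term has a standardised effect of 1.960 + 0.842 = 2.802. Multiplying by √1.0243 or √1.05 gives 2.835 or 2.871, which is power of about 80.9% or 81.9%.

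A simulation agrees (3 × 1,000 people, 8 panels of 10, ratings rounded to 1-5, 1,500 runs per case):

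| a | SE without → with | variance ratio | power, 0.08 shift | rejection under the null |
|---|---|---|---|---|
| 0.10 | 0.0265 → 0.0262 | 1.023 | 82.5% → 82.9% | 0.057 → 0.056 |
| 0.20 | 0.0265 → 0.0259 | 1.047 | 83.9% → 85.4% | 0.048 → 0.051 |

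**2. Logistic model.** Simulation with 3 × 1,000 people, person SD 1.0, baseline logit −0.5, a true odds ratio of 1.50 given person and advertisement, and 60 runs per case:

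| Advertisement logit SD | Odds ratio: no term / panel / advertisement | Mean z: no term / panel / advertisement |
|---|---|---|
| 0.5 | 1.48 / 1.48 / 1.51 | 7.40 / 7.47 / 7.47 |
| 1.0 | 1.41 / 1.42 / 1.51 | 7.15 / 7.36 / 7.36 |

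Averaging 1.50 directly over a normal advertisement effect gives 1.467 and 1.399. The fitted values match these, and 1.50, within Monte Carlo error (SE 0.007-0.008 on the log scale). The z statistic rises by 7.467/7.398 − 1 = 0.9% and 7.363/7.153 − 1 = 2.9%. A panel term gives the same z but leaves the odds ratio averaged over advertisements.

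A second simulation (2 × 600 people, 10 of 40 advertisements each, person SD 1.5, true log odds ratio 0.30, 48 runs per case) shows what happens to the standard error:

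| Advertisement logit SD | Odds ratio without → with | SE of log odds ratio without → with | z |
|---|---|---|---|
| 0.5 | 1.34 → 1.36 | 0.0943 → 0.0990 | +0.2% |
| 1.0 | 1.30 → 1.37 | 0.0846 → 0.0994 | +1.1% |
| 1.5 | 1.25 → 1.36 | 0.0744 → 0.1004 | +2.7% |

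With person SD 0.7 and advertisement SD 1.0, z rises by 3.3%. The standard error goes up, because the log odds ratio itself moves away from zero; only the ratio of the two improves.

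**The case against.** The strongest reply is that no inference in the plan is wrong. Panels are randomised, the null is unaffected, the power gain is a point or two at most in the central cases, and an odds ratio averaged over advertisements is a fair answer to a question about all claims together. All of that stands, and it sets the weight of the point.

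Three further objections also stand in part. Claim meaning score is undefined; if it varies by advertisement it already takes up some of the between-advertisement variation, and the simulations do not include it. An odds ratio conditional on advertisement is a single common value, so it assumes that use status acts alike on every advertisement. And the mean-score step names no model at all, so the missing term there is one of several unstated details. The logistic model is different: its covariates are listed, and the advertisement is not among them.

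A reader might infer more than the documents support:

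- *Bias.* That use status is confounded with advertisement. Random assignment to panels rules this out when ratings are complete.
- *Type I error.* That ratings are treated as independent. The plan does not say so, the logistic model accounts for repeated measures, and the simulated null rejection rates stay near 5%.
- *Precision of the odds ratio.* That the term narrows its interval. The standard error of the log odds ratio rises.
- *Skipped ratings.* That accepting surveys with up to a quarter of outcome items unanswered distorts the comparison. This needs skipping that depends on both use status and advertisement, and nothing in the documents suggests that pattern.

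**Conclusion.** The point holds as a minor, low-cost improvement and not as an error. With the assumed 8 panels of 10 and a 30% person share, omitting the advertisement adds about 2.4% or 5.0% to the variance of the use-status mean difference when advertisements explain 10% or 20% of rating variance, and about 1.4% or 2.9% with 2 panels. In the logistic model the main benefit is a defined target. The odds ratio differs by an amount that depends on how much advertisements vary (1.48 against 1.51 at logit SD 0.5, 1.41 against 1.51 at 1.0), and by less if claim meaning score absorbs part of it. The gain in z is about 0-3%. These sizes rest on assumed variances and on panels differing in content; that the term is absent is plain from the text.

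**What to change.** In the Analytic Plan:

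1. Add an advertisement effect to the random-effects logistic model beside the participant random intercept. It may be crossed random or fixed; crossed random is safer if some advertisements draw nearly all-yes or all-no responses. A panel term is not a substitute, because it leaves the odds ratio averaged over advertisements.
2. State that the odds ratio is conditional on advertisement and assumes a common use-status effect across advertisements.
3. Compare mean scores with a linear mixed model that has three-level use status, a participant random intercept and an advertisement effect. This also settles the unit of analysis.

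The cost is SAP wording and one model term in SAS V9.4, which is already planned. The advertisement identifier must be kept in the analysis file, as the per-advertisement step already requires. No new data and no change to the survey are needed.

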(Approximately 1,000 current CBD users; 1,000 ever CBD users, and 1,000 non-users). Therefore, the survey will begin with a short screener survey about CBD use.

Screener

All interested individuals will be able to complete our screener. Interested individuals will click on the link to the survey and be routed to a website to review consent language and complete the survey. Participants will complete a one-minute screener to determine if they are eligible for the full survey based on their age and CBD use. If eligible, they will be consented and then proceed to take the survey.

Inclusion Criteria

- Age 18-65
- US Residents

Exclusion Criteria

- Non-English speakers
- Younger than 18 or older than 65
- Not US residents

Full Survey

Inclusion Criteria

- Age 18-65
- US Residents
- Satisfies one of the following categories:
 - o 1. Current CBD users
 - o 2. Ever CBD users
 - o 3. Non-CBD users
- Members of the AmeriSpeak[™] panel

Exclusion Criteria

- Non-English speakers
- Younger than 18 or older than 65
- Not members of the AmeriSpeak[™] panel

Sample Size

Based on a response rate of 34% and prevalence estimates for CBD use between 14-25%, we
estimate a random sample of about 22,000 adults will be invited to complete the screener survey to
achieve our goal of 3,525 completed surveys.

Interventions and Interactions

Individuals will be contacted by AmeriSpeak™ to participate in the survey, and if interested, will complete a screener to determine eligibility. After completing the screener, participants who are ineligible will be thanked for their time and will exit the survey. They will not receive an incentive for completing the screener. Participants who meet eligibility criteria will be invited to complete the full survey. The full survey will last

approximately 15-20 minutes. After completing the survey, participants will receive a small incentive in the form that they've agreed to with their panel (approximately \$5).

Outcome Measure(s)

Outcome Measure

This is a post-test only experimental design. The primary outcome is *claim perception* by CBD use status. We will determine if advertisements are interpreted by consumers in one or more ways that the FDA has determined are prohibited (i.e. drug effect; FDA approved/endorsed; dietary supplement; food additive; false/misleading-youth; false/misleading-science). We will assess this using the following items, all of which will use a 5-point response scale, (1) Not at all to (5) Extremely.

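### The logistic model adjusts the use-status odds ratios for sex, race/ethnicity and chronic conditions but omits age, which is recorded for every participant

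*Combined protocol and SAP*

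**What the plan says.** All references are to the combined protocol and SAP.

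- **How the groups arise.** Under Design, what is randomised is the set of advertisements: "participants will be randomly assigned to a panel consisting of up to 10 CBD advertisements". Use status is a characteristic that respondents report. Under Subjects Selection Criteria it also shapes the sample: "We will oversample CBD users so the final respondent sample is comprised of 1/3 current CBD users", with the other two thirds being ever users and never users.
- **Age is collected.** Design: "To assess eligibility, participants will be asked their age and several questions about CBD use". The Screener section says the same, with respondents found "eligible for the full survey based on their age and CBD use". Under Subject Recruitment Methods: "Participants will be recruited and screened by AmeriSpeak™ according to age (18-65) and CBD use status". Apart from a general statement under Outcome Measure(s) that demographics will be asked, age appears only as the eligibility limit.
- **The analyses.** The Analytic Plan has three parts: mean scores for each claim type by use status; chi-squared tests of users against non-users for each advertisement; and one random-effects logistic model over all claims, "as a function of CBD use status, sex, race/ethnicity, claim meaning score, and chronic health conditions". The first two name no covariates. Group differences in claim perception are to be read from the model's odds ratios.
- **The goals.** Goal 1 asks whether use status is associated with claim perception. Goal 3 is to "explore participant characteristics (beyond use status) that are associated with interpreting a claim" as one of the prohibited types.

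No section describes survey weights, an age-adjusted analysis or an age-based sensitivity analysis.

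**The concern.** The logistic model is the only planned analysis that adjusts the use-status comparison. By including sex, race/ethnicity and chronic conditions, the plan accepts that the use groups may differ in background in ways that matter for how an advertisement is read. Age belongs to the same class of variable. It precedes CBD use, so it is not a consequence of use that ought to be left out, and the eligible range covers 47 years (65 − 18). The plan gives no reason for omitting it.

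Two things are at stake. First, if the use groups differ in age, and age is related to how claims are read, an odds ratio presented as adjusted for participant characteristics still contains an age contribution. Chronic conditions may absorb part of this but do not stand in for age. Second, the covariate list is written as complete, so the analysis serving goal 3 leaves out a basic characteristic that is on file for every respondent.

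**Working it through.** The plan states no figure on this point, so there is none to reproduce. The check has two parts.

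**1. Is age handled anywhere?**

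| Element of the plan | Age used? |
|---|---|
| Screener and eligibility | Yes, as the 18-65 limit only |
| Mean scores by use status | No covariates named |
| Chi-squared tests, users v non-users | No covariates |
| Random-effects logistic model | Five terms listed, age not among them |
| Weights or sensitivity analyses | None described |

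Age is therefore collected but enters no planned analysis.

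**2. What would the omission do?** Bias requires age to be related both to use status and to claim perception. The documents give neither relation. The following is an illustration in which every input is assumed:

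- no true use-status effect;
- two age strata, younger and older;
- 40% of the older stratum read the advertisement as prohibited;
- 30% of non-users are younger.

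Let *a* be the age odds ratio. The proportion in the younger stratum is p₁ = o/(1 + o), with o = (0.40/0.60) × *a*. Each group's proportion is q × p₁ + (1 − q) × 0.40, where q is its younger share.

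- **No age difference (q = 30% in both groups):** the two proportions are equal and the crude odds ratio is 1.00, whatever *a* is.
- **Users 40% younger, *a* = 2:** o = 1.333, p₁ = 0.571. Users: 0.40 × 0.571 + 0.60 × 0.40 = 0.469. Non-users: 0.30 × 0.571 + 0.70 × 0.40 = 0.451. Crude odds ratio = 1.07.
- **Users 50% younger, *a* = 2:** users 0.486, non-users 0.451, crude odds ratio 1.15.
- **Users 60% younger, *a* = 3:** o = 2, p₁ = 0.667. Users: 0.60 × 0.667 + 0.40 × 0.40 = 0.560. Non-users: 0.30 × 0.667 + 0.70 × 0.40 = 0.480. Crude odds ratio = 1.38.

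These are crude odds ratios for one response per person. The planned model has repeated responses, a random effect and other covariates that may take up part of an age effect. The figures show the mechanism and that zero is within the range. They do not estimate the bias in the model's odds ratio.

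**The case against.** The strongest reply is that the plan asks a descriptive question. The survey is cross-sectional, goal 1 speaks of association, and no section claims that CBD use causes a reading of the advertisements. How actual users and non-users read them is a legitimate question, and unadjusted means and chi-squared tests answer it. An age contribution is then part of the difference, not an error in it. This stands for those two analyses. It does not cover the logistic model, which already adjusts for background characteristics and from whose odds ratios group differences are to be read.

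A second reply is that goal 3 is exploratory and age can be added at reporting, since it is held. That is true, but a term chosen after the data are seen is weaker than one named now.

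Two stronger readings are tempting and are not supported.

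- **That sampling in thirds by use status, without age balance, causes the problem.** Selecting on use status does not create an age difference between use groups; any such difference exists in the population and would appear without oversampling. Forcing age balance would make each group less representative of the people it describes.
- **That the bias reaches about two standard errors.** Suppose the share under 35 differs by 15 to 25 points between groups, and under-35s differ by 10 to 20 points in reading an advertisement as prohibited. The product runs from 0.15 × 0.10 = 1.5 points to 0.25 × 0.20 = 5.0 points. Against √(2 × 0.25/1000) = 2.24 points, that is 0.7 to 2.2 standard errors. But both gaps are assumed, and the upper end takes both at their maximum. The standard error matches no planned analysis: the model pools up to 10 advertisements per person, and each chi-squared test uses only those shown that advertisement. At an assumed 250 v 250, the standard error is √(2 × 0.25/250) = 4.5 points, and 5.0 points is 1.1 standard errors.

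**Conclusion.** The point holds for the logistic model. Use status is not randomised, age is recorded for everyone, and the only adjusted analysis omits it while including comparable characteristics. The use-status odds ratios can therefore carry age differences between the groups. Whether they do, and by how much, cannot be determined from the documents; the bias could be zero. It depends on two relations that the plan does not describe: age with use status, and age with claim perception.

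The gap under goal 3 rests on no assumption: the model as listed cannot report age.

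A reader might infer that the observed use-status differences will be age effects, or that the unadjusted comparisons are invalid. Neither follows. The first needs data that the documents do not contain, and the second treats a descriptive comparison as a causal one. This is a low-cost improvement to a stated analysis, not a fault that undermines the survey.

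**What to change.** In the Analytic Plan:

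1. Add age to the random-effects logistic model, either as a continuous term or in pre-specified categories (for example 18-34, 35-49 and 50-65), and state the form now.
2. Report the age odds ratio with the other characteristics under goal 3.
3. Keep the unadjusted means and chi-squared comparisons, labelled as descriptive, and report age-adjusted use-status comparisons beside them for both the mean scores and the proportions.

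Adding a covariate to a logistic model can shift an odds ratio even without confounding. Adjusted and unadjusted results are therefore best compared on the scale of means or proportions.

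The cost is a change of SAP wording, one added covariate (one or two parameters) and a few more table entries. No new data, sample size change or fieldwork change is needed.
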